# Neuromodulation for Children with Cystic Fibrosis

## Experiencing Chronic Abdominal Pain

NCT05515250

Last review date 07/25/2023

**STUDY PROTOCOL:** Eligible participants will be recruited from the gastroenterology or Cystic Fibrosis clinics at Cardinal Glennon Hospital, Saint Louis University and Saint Louis Children's Hospital at Washington University in Saint Louis. Consent to participate and a detailed history, physical examination and laboratory tests for stool calprotectin will be obtained at the participants' clinical management site. A global assessment of abdominal pain will be used to rate its severity. Participants will be allowed to continue medication regimens that they are on prior to enrollment. No adjustments in medications will be allowed during the 3-week study period unless deemed necessary by the CF care team. Also, no new medications or OTC treatments will be allowed during the 3-weeks trial of PENFS unless deemed necessary by the CF care team. The use of all medications will be carefully monitored each week for future evaluation.

Following screening evaluation, enrolled participants will complete questionnaires and have the initial PENFS device placed by a trained health care professional. Device placement will then be done at the gastroenterology clinic at Cardinal Glennon Hospital to which participants will return every 7 days for a total of 3 visits for device replacement and completion of questionnaires. Three different devices will be placed in total (at baseline, at the end of week 1, and at the end of week 2). Following each visit and at week 8, participants will complete follow-up pain, CFQ-R, IBS-SSS, and PedsQL GI symptom scale administered in person by the study clinical coordinator at the clinical management site. The PI and sub-investigators at each clinical site will review adverse events on a continual basis to watch for unexpected safety signals.

Table 1 presents the expected timeline. The total length of the study, from screening of the first participant to the end of the study, is expected to be approximately 12 months

	Screening/ baseline	End of Week 1	End of Week 2	End of Week 4 **	8-week follow- up **
Informed Consent/enrollment	X				
Eligibility assessment	X				
Demography and Medical history	X				
Check Current Medication	X	X	X	X	X
IB-Stim Placement	X	X	X		
Pain Score*	X	X	X	X	X
CFQ-R*	X	X	X	X	X
IBS-SSS*	X	X	X	X	X

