PedsQL GI symptom scale Version 3.0*	X	X	X	X	X
Stool Calprotectin	X a			X b	

**STATISTICAL PLAN**(in conjunction with the AHEAD Institute at St. Louis University): The primary endpoint for this study is the change in the abdominal pain scores from baseline to study exit. The secondary endpoints will be the change in the IBS-SSS (Symptoms Severity Scale), CFQ-R, and PedsQL Gastrointestinal symptom scale from baseline to study exit. The median pain scores will be computed at the three time points in the study (baseline, at 4 weeks and at 8 weeks) and compared using the non-parametric Kruskal Wallis test. Ad-hoc pairwise comparisons will be done using the Dwass, Steel, Critchlow-Fligner multiple comparison procedure (10,11). Trends in these indices over time will be compared using mixed models adjusting for repeated measures. These statistics will also be computed for the secondary endpoints. REDCap (Research Electronic Data Capture), a secure web-based application or password protected excel, will be used for data management and storage. P-values < 0.05 are considered significant. All analysis will be two-sided and completed in SAS 9.4 or the current version of SAS at the time of the study (SAS Institute Inc., Cary, NC, USA).

Due to less-than-optimal numbers of participants, this study was closed after enrolling one patient. Therefore, the above statistical methods could not be applied.

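### Kruskal-Wallis and Dwass-Steel-Critchlow-Fligner treat the same children's scores at three times as independent groups; with positive within-child correlation the p-values are too large

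*Combined protocol and SAP*

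**What the plan says.** Under STUDY PROTOCOL the combined protocol and SAP describes a single treated group: "enrolled participants will complete questionnaires and have the initial PENFS device placed by a trained health care professional". No comparator is mentioned. The same children are then assessed repeatedly: "Following each visit and at week 8, participants will complete follow-up pain, CFQ-R, IBS-SSS, and PedsQL GI symptom scale".

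Under STATISTICAL PLAN the endpoint is a within-child quantity: "The primary endpoint for this study is the change in the abdominal pain scores from baseline to study exit". The analysis compares median pain scores at three times, "baseline, at 4 weeks and at 8 weeks) and compared using the non-parametric Kruskal Wallis test", and continues: "Ad-hoc pairwise comparisons will be done using the Dwass, Steel, Critchlow-Fligner multiple comparison procedure". A further sentence adds a model: "Trends in these indices over time will be compared using mixed models adjusting for repeated measures". The whole set is carried over to IBS-SSS, CFQ-R and PedsQL GI: "These statistics will also be computed for the secondary endpoints". Tests are two-sided at 0.05.

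No paired rank test is named, and no sentence says which of these analyses decides the primary endpoint. The section ends by reporting that "this study was closed after enrolling one patient" and that the methods could not be applied.

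**The concern.** Kruskal-Wallis and DSCF pool the observations, rank them, and judge differences between groups against the variance expected if every observation were independent. Here each child contributes one score to every group. The tests discard the pairing on which the endpoint is built.

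The direction matters. When a child's scores are positively correlated, stable differences between children inflate the variance the test uses, but they cancel from the comparison between times. The statistic is then too small and the p-value too large. The danger is a real improvement that goes undetected, with a non-significant rank test read as no change. A second danger is that the rank tests and the mixed model disagree, with no rule for which one counts.

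**Working it through.** **Inputs from the documents.** One group; three times (baseline, week 4, week 8); two-sided alpha 0.05. The plan states no sample size, power, SD, effect size or within-child correlation, so there is no design figure to reproduce.

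**Assumed inputs.** Number of children n from 10 to 40; equal correlation rho between times; normal scores rounded and clipped to 0–10; SD 2; where there is an effect, an equal drop at weeks 4 and 8; study exit taken as week 8.

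**Step 1: why the test is conservative.** For equally correlated scores, the variance of a difference between two mean ranks is (1 − rho_S) times the value for independent groups, where rho_S is the rank correlation. For normal scores rho_S = (6/π)·arcsin(rho/2). In large samples under no change, Kruskal-Wallis therefore behaves as (1 − rho_S) times a chi-square on 2 df. The upper tail of that chi-square is exp(−x/2), so the true size at nominal 5% is

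size = 0.05^(1/(1 − rho_S)).

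- rho = 0.3: rho_S = 0.288; 0.05^(1/0.712) = 1.5%
- rho = 0.5: rho_S = 0.483; 0.05^(1/0.517) = 0.31%
- rho = 0.7: rho_S = 0.683; 0.05^(1/0.317) = 0.008%

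**Step 2: size in small samples.** Simulation under no change, 20,000 replicates per cell, rounded 0–10 scores, nominal 5%. DSCF is the rate of any of the three pairs being significant.

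| rho | Kruskal-Wallis, n=20 | Kruskal-Wallis, range over n=10, 20, 40 | DSCF, n=20 | Friedman, n=20 |
|---|---|---|---|---|
| 0 | 4.8% | 4.5–4.9% | 4.7% | 4.9% |
| 0.3 | 1.7% | 1.6–1.8% | 1.7% | 4.9% |
| 0.5 | 0.45% | 0.45–0.73% | 0.48% | 4.8% |
| 0.7 | 0.06% | 0.03–0.17% | 0.08% | 4.8% |

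At rho = 0 the nominal level is recovered, so the shortfall comes from the correlation. With continuous scores at n=20, other positive structures are also conservative. Kruskal-Wallis size is 0.2% for a first-order autoregressive pattern with rho 0.7. It is 1.8% when baseline is weakly correlated (0.2) with two strongly correlated follow-ups (0.8), and 0.7% with unequal variances and rho 0.5. Negative correlation reverses the direction: at rho = −0.3 the size is 9.5%.

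**Step 3: power.** 10,000 replicates per cell (Monte Carlo standard error at most 0.5 points). Entries are for rho 0.3 / 0.5 / 0.7.

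| Setting | Kruskal-Wallis | Friedman | Mixed model |
|---|---|---|---|
| n=10, 0.5 SD drop | 11 / 8 / 5% | 19 / 24 / 38% | not tabulated |
| n=20, 0.5 SD drop | 25 / 23 / 17% | 36 / 50 / 71% | 44 / 59 / 79% |
| n=30, 0.8 SD drop | 90 / 92 / 95% | 91 / 98 / 100% | not tabulated |

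The mixed model here is the balanced compound-symmetry F test with time as a category. Near-normal, equally correlated data favour it.

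Baseline against week 8, each method adjusted for three pairs:

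| Setting | DSCF | Signed-rank with Holm |
|---|---|---|
| n=20, 0.5 SD drop | 15 / 13 / 9% | 24 / 36 / 57% |
| n=30, 0.8 SD drop | 75 / 78 / 83% | 87 / 96 / 100% |

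Repeat simulations agreed with these power figures to within about three points. As a boundary case, at rho = 0 with n=20 and a 0.5 SD drop (continuous scores), Kruskal-Wallis has 31% power and Friedman 26%. The paired test therefore gains only when there is correlation to exploit.

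**The case against.** The strongest reply has four parts.

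- **The plan already contains a valid analysis.** The mixed model adjusts for repeated measures, and the indices it refers to naturally include pain. In a one-group study, trend over time is close to the main question. This stands in part: the model is sound, and making it primary is one of the two remedies below. It is not a cure as written, because the comparison of the three times is given to the rank tests and nothing says which result governs.
- **The study closed after one patient.** No test was run, no reported result is affected, and the documents announce no further use of the plan. This stands in full. It limits the consequence but does not make the method right.
- **The error is on the safe side and the figures are assumed.** Both are true. The plan makes no power claim for the error to contradict, and the pain scale's range is not given. With n=30 and a 0.8 SD drop, the loss in the overall test is small (90% against 91% at rho 0.3).
- **Friedman with three adjusted pairs is more than the endpoint needs.** The primary endpoint is one contrast, baseline to study exit. This is fair, and it favours an analysis built on that contrast.

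**Conclusion.** The point holds. Two independent-group procedures are planned for repeated scores from the same children, against an endpoint defined as within-child change, and the same mismatch is carried to the three secondary scales. Given positive within-child correlation, the p-values are too large. For 20 children and a 0.5 SD drop, the loss of power against Friedman is 11, 27 and 54 points at rho 0.3, 0.5 and 0.7 (36−25, 50−23, 71−17). It shrinks as samples and effects grow, and as the correlation approaches zero.

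That the tests are the wrong kind follows from the documents alone. The direction needs positive correlation, which is the natural expectation for one child's scores but is not stated in the plan. The magnitudes depend on the assumed n, correlation, effect and scale. The wording should be corrected before the plan is reopened or reused; nothing already reported needs revision.

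**What to change.** Say which visit is study exit, and name one primary analysis that uses the pairing. Either:

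- **(a) Paired rank analysis.** Replace Kruskal-Wallis with the Friedman test, and DSCF with Holm-adjusted Wilcoxon signed-rank tests on within-child change. Report the Hodges-Lehmann estimate with its 95% confidence interval. If the primary claim is confined to the single baseline-to-exit contrast, one signed-rank test is enough and needs no adjustment over pairs.
- **(b) The mixed model already planned.** Make it primary, with time as a category, and report the baseline-to-study-exit contrast with its 95% confidence interval as the primary result.

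Apply the same choice to IBS-SSS, CFQ-R and PedsQL GI, and label any remaining analysis as supportive.

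The cost is about two sentences of wording. Both options run in SAS, which the plan already specifies. The trade-off is that Friedman needs all three scores from every child, whereas the mixed model can use incomplete cases but leans more on its distributional assumptions when n is small.

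### Does a mixed model for trends over weeks 0 to 8 misstate the effect when stimulation stops at about week 3?

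*Combined protocol and SAP*

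**What the plan says.** The STATISTICAL PLAN paragraph defines the target: "The primary endpoint for this study is the change in the abdominal pain scores from baseline to study exit". It then names the times of analysis: "The median pain scores will be computed at the three time points in the study (baseline, at 4 weeks and at 8 weeks". These are compared by the Kruskal-Wallis test, and for pairs of time points "Ad-hoc pairwise comparisons will be done using the Dwass, Steel, Critchlow-Fligner multiple comparison procedure". The mixed model gets one sentence: "Trends in these indices over time will be compared using mixed models adjusting for repeated measures". That sentence gives no form for time, no list of visits, no covariance and no contrast. The same statistics are to be repeated for the secondary endpoints.

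The STUDY PROTOCOL paragraphs give the treatment schedule: "Three different devices will be placed in total (at baseline, at the end of week 1, and at the end of week 2", and "participants will return every 7 days for a total of 3 visits for device replacement and completion of questionnaires". They also refer to a three-week period of stimulation ("no new medications or OTC treatments will be allowed during the 3-weeks trial of PENFS"). The third device would therefore come off at about week 3. Table 1 collects the pain score at five visits ("Pain Score* X X X X X"): baseline and weeks 1, 2, 4 and 8.

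The paragraph ends by recording that the study closed after one participant and that these methods could not be applied.

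**The concern.** The word trends suggests a straight line through time. Treatment is on for weeks 0 to 3 and off for weeks 3 to 8, so the true course is unlikely to be straight. Over visits at 0, 1, 2, 4 and 8 weeks the last visit dominates the fit. A fast and lasting drop would then be flattened, and a drop followed by a rebound could give a rising line. The mixed model is also the only named analysis that allows for the same child being measured repeatedly, so its target matters. If it were aimed at the wrong quantity, a real benefit could be missed or reported as worsening. Finally, there is one arm and the indices have different scales, so it is not obvious what is compared with what.

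**Working it through.** The documents give no sample size, effect size or SD, so there is no figure of the plan's own to reproduce. The profiles, D = 0.60 SD, n = 20 and correlation 0.5 below are assumptions. Data are taken as complete, and exit as week 8, the last visit.

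**Linear time over the five Table 1 visits, equal correlation.** Mean time is (0+1+2+4+8)/5 = 3. The deviations are -3, -2, -1, 1 and 5, and their sum of squares is 9+4+1+1+25 = 40. The slope weights are deviation/40: -0.075, -0.05, -0.025, 0.025 and 0.125. Week 8 supplies 25/40 = 62.5% of the sum of squares.

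Slope × 8 for a lasting drop of size D (true exit change -1.00 D):

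- Full drop by week 1: 8 × -(-0.05 - 0.025 + 0.025 + 0.125) D = -0.60 D, which is 40% too small. With D = 0.60 SD this is -0.36 SD.
- Drop building linearly to week 3: 8 × -(-0.05/3 - 0.025 × 2/3 + 0.025 + 0.125) D = -0.93 D, 7% too small.
- Drop appearing only by week 4: 8 × -(0.025 + 0.125) D = -1.20 D, 20% too large.

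With a correlation that decays at 0.8 per week, the same three cases give -0.92 D, -0.98 D and -1.04 D.

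Rebound, mean profile (0, -0.3, -0.6, -0.4, 0) SD: 8 × (0.015 + 0.015 - 0.010 + 0) = +0.16 SD. The true exit change is 0. The standard error of slope × 8 is 8 × √[(1 - 0.5)/(40 × 20)] = 0.20 SD, so the estimate lies 0.8 standard errors from zero and would be significant only about 12% of the time.

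Where some benefit remains at week 8, the slope has the wrong sign only if less than 40% of an immediate drop, or less than 6.7% of one building to week 3, is left. Under the decaying correlation the limits are 8.2% and 1.7%.

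Power for D = 0.60 SD, n = 20 (noncentral t, 19 df):

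- Immediate lasting drop: the slope has 0.36/0.20 = 1.8 standard errors. The week-8 contrast has 0.60/√(2 × 0.5/20) = 0.60/0.224 = 2.68. Power is 40% against 72%.
- Gradual drop (0, -0.2, -0.4, -0.6, -0.6) SD: slope × 8 = -0.56 SD, or 2.8 standard errors. Power is 76% against 72%, so the slope does no worse.

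**Linear time over the three visits named in the statistical plan.** Mean time is 4, the deviations are -4, 0 and 4, and the sum of squares is 32. The weights are -1/8, 0 and +1/8. Hence slope × 8 = (week 8) - (baseline), whatever the value at week 4. Its variance is 64 × (1 - ρ)/(32n) = 2(1 - ρ)/n, the same as for the contrast. Understatement, wrong sign and power gap are all zero. The equality of slope × 8 and the week-8 change also holds under a random slope and under the decaying correlation.

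**Visit as a categorical factor.** The week-8 contrast equals the true exit change for every profile.

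**The case for a change.** The best case for a change is this. The wording readily admits a linear term, Table 1 offers five visits, and the plan ties the three time points to the medians and the Kruskal-Wallis test, not expressly to the model. An analyst could therefore choose between slope and visit contrasts after seeing the data, and the answers could differ. The rank tests do not rescue the matter, because they treat repeated measurements on the same child as independent. One sentence would close the gap.

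Part of this stands. The form of time, the visits and the contrast are not written down, and a five-visit slope need not equal the endpoint. The rank tests do ignore the pairing, but that is a separate point about those tests and does not show that the mixed model is misdirected.

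The rest does not carry. Both the linear form and the five visits have to be supplied by the reader. The three-visit slope gives no weight to week 4, so it would miss a benefit lost by week 8. So would the exit contrast, because the endpoint itself is defined at exit. The rebound example has no true sign to reverse, since its exit change is zero. The complaint about scales and comparison falls away on a natural reading: each index is analysed separately, and its values are compared across time within the single arm.

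**Conclusion.** The arithmetic of the concern is correct for one reading of one sentence, and the documents do not commit to that reading. On it, the error after a lasting drop runs from 40% too small to 20% too large under equal correlation, and from 8% too small to 4% too large under the decaying correlation. At the three time points the statistical plan names, it is exactly zero. No rule stated in the plan is shown to give a wrong result. What is left is a gap in detail of the kind that analysts fill sensibly: with an endpoint defined as change to exit and a mixed model for repeated measures, modelling by visit and reading off the exit change is the natural choice. With one participant enrolled, no result was affected. The conclusion assumes complete data and week 8 as exit; the effect sizes, profiles, n and correlations serve only to illustrate the size. No change to the plan is called for.
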